1.0 Research Design

1.1 Purpose/Specific Aims

A. Objectives

In the **current study** we propose a proof-of-concept experimental test of PTBT and its ability to modify stress-precipitated puff topography, and in turn, acute smoking reinforcement. Specifically, emotionally-distressed daily smokers ($N=88$) will be randomized to either PTBT or Control (Sham) Training. After the training day, participants will complete a stress-precipitated smoking trial where they will undergo an acute laboratory stress induction and smoke using the assigned training. We propose the following specific aims:

Aim 1 (Target Engagement): To evaluate PTBT as a strategy to “engage” (modify) puff topography -- a putative biobehavioral target of smoking reinforcement. Following stress-induction, we hypothesize that PTBT, compared to Control, will result in significant changes in puff topography, namely: (a) smaller average puff volume (mL), (b) shorter average puff duration (sec), and (c) longer inter-puff intervals (sec).

Aim 2 (Acute Clinical Outcomes): To evaluate whether PTBT produces acute clinical changes in stress-precipitated smoking reinforcement. Following stress-precipitated smoking trial, we hypothesize that PTBT, compared to Control, will result in significantly less acute smoking reinforcement, indexed by: (a) greater reductions in expenditures and consumption of hypothetical cigarettes smoked within the same context (e.g., PTBT or ad-lib) and (b) lower self-report cigarette satisfaction/reward (self-report) post-smoking.

Aim 3 (Explore Mechanisms of PTBT). To explore cardiac vagal control (CVC) as a biological mechanism of PTBT. We will explore whether there are differences in CVC (respiratory sinus arrhythmia) between smokers in PTBT compared to Control. We hypothesize that PTBT (vs Control), will produce greater reductions in CVC, as compared to baseline CVC, during stress-precipitated smoking.

This is the first study to test whether an integrated theoretically-based biobehavioral paradigm can modify puff topography and subsequent smoking reinforcement. This addresses the need for **innovative approaches to decrease acute smoking reinforcement**. If associated with reduced smoking reinforcement, this paradigm could inform pre-cessation efforts designed to better prepare emotionally-distressed smokers for quitting.

B. Hypotheses / Research Question(s)

Smoking among adults with emotional distress is a recognized tobacco health disparity. Smokers with emotional distress are particularly vulnerable to **smoking reinforcement** due to various biopsychological factors that contribute to deficits in emotion regulation and reward processing, which undermine cessation efforts. Better preparing smokers for cessation (prior to a quit attempt) is essential to improve outcomes in emotionally-distressed smokers who require additional coping strategies to address affect-driven smoking.

A critical driver of smoking reinforcement is HOW a cigarette is smoked (i.e., puff topography). The timing and intensity of one's puffing can titrate or maximize the cigarette's rewarding effect. Our group has identified **puff topography as a novel biobehavioral “target” mechanism of smoking reinforcement** in emotionally-distressed smokers. We have found that topographical components of puffing (e.g., shorter inter-puff intervals, longer puff durations) are linked to heightened smoking reinforcement in emotionally-distressed smokers, but not in control smokers. Emotionally-distressed smokers also take larger and more rapid initial puffs at the start of a cigarette – maximizing immediacy and intensity of reward.

Although largely considered a behavioral phenotype of smoking reinforcement, inherent in puffing behavior are corresponding changes in cardiorespiratory parameters (e.g., cardiac vagal control [CVC])

that may promote self-regulation and reduce craving. We recently proposed an integrated psychophysiological model of emotional distress and smoking, wherein impaired smoker CVC not only implicates physiological homeostasis, but also influences addiction-relevant processes, including impaired higher-order cognitive processes needed for self-regulation and psychological functioning (e.g., reduced anxiety and stress). Yet, under certain time-sensitive contexts (e.g., stress), emotionally-distressed smokers may puff in a way that enhances CVC, resulting in acute self-regulatory benefits, and in turn paradoxically amplify the reinforcing value of each puff. Thus, a biobehavioral intervention that could “engage” (modify) puff topography has the strong potential to reduce the reinforcing value of cigarettes in emotionally-distressed smokers.

Informed by our biobehavioral framework, we developed a **Puff Topography Biofeedback Training (PTBT)**, a modified application of heart rate variability biofeedback to change puff topography. PTBT is a 30-min training that teaches smokers to adjust their puffing to a pace that is designed to minimize CVC in order to attenuate acute self-regulatory, emotional, and craving-reductions associated with smoking. Thus, PTBT is a theoretically-informed, well-specified paradigm designed to directly target puff topography – a mechanism of smoking reinforcement, which directly aligns with the NIH’s Science of Behavior Change (SOBC) and experimental therapeutics initiatives.

1.2 Research Significance

1. This is the first study to develop and test a **puff topography biofeedback training (PTBT)**. Participants will receive real-time feedback regarding puffing (e.g., when to inhale/exhale, breath duration, and inter-puff interval). PTBT was designed based on an integrated theoretical behavioral and psychophysiological model of smoking reinforcement, and thus aims to address learning-based behavioral aspects of puffing (by promoting extinction learning/new learning), in addition to altering a physiological mechanism of puffing (CVC). Therefore, PTBT is a promising theoretically-based intervention, that if supported by this proposed experimental study, would be well-positioned for progressive translation into intervention efficacy testing, consistent with NIH initiatives.^{49–51}
2. There is increasing recognition that preparing smokers for cessation (prior to a quit attempt) is essential to improve outcomes,⁵² particularly in smokers with emotional distress who may require additional coping strategies to address affect-driven smoking.⁵³ If PTBT is associated with reduced smoking reinforcement, this paradigm could inform treatment effects designed to prepare emotionally-distress smokers for quitting.⁵² Notably, existing interventions that successfully attenuate *pre-cessation* smoking reinforcement are primarily pharmacological in nature (e.g., nicotine replacement,⁵⁴ varenicline⁵⁵), while behavioral interventions targeting smoking reinforcement are generally used during the *post-cessation* period (e.g., contingency management,⁵⁶ behavioral activation/behavioral economic-based approaches⁵⁷). Thus, the current study would address a gap in the provision of evidence-based behavioral interventions that target *pre-cessation* smoking reinforcement, which has the potential to improve cessation outcomes in vulnerable smokers (emotionally-distressed).

1.3 Research Design and Methods

This study is an experimental, between-subjects test of biofeedback puff topography training (relative to sham training) in reducing stress-induced smoking reinforcement. Specifically, combustible cigarettes smokers ($n = 80$) will be randomized to receive puff topography biofeedback ($n = 40$) or sham training ($n = 40$) prior to exposure to a laboratory stressor paradigm. Stress-precipitated smoking behavior will be assessed directly after the stressor task, wherein participants will be given the instructions to smoke utilizing their assigned puff training. Smoking reinforcement will be measured using a multi-method approach, including self-report, psychophysiology, and behavioral indices (see Measures). Outcome variables include: (1) puff topography indices (averages, trajectory) and (2) reinforcer pathology indices (delay reward discounting, cigarette demand, urges, affect, and smoking enjoyment).

A. Research Procedures

See **Figure 3** for an overview of the experimental procedures. Participants will complete a telephone interview to verify key exclusion/inclusion criteria. Participants who appear to be eligible will be scheduled for a remote assessment session. If eligible following the remote session, participants will be scheduled for two in-person visits on consecutive days. For standardization (internal validity), all in-person visits will be scheduled to occur ~4hrs following the estimated time of participants' first cigarette of the day. Participants will be informed that they will smoke their second daily cigarette during the lab visit and instructed to avoid behaviors that may confound CVC (e.g., vigorous physical activity or consumption of caffeine within 2 hr; alcohol use within 12 hr).

Baseline Assessment (Remote Visit): Staff will obtain written informed consent, after which participants will complete an eligibility assessment (see **Table 1**). They will then complete the baseline assessment battery (see **Table 1**).

[figure not shown]
Training Visit (V1): Participants will be screened for final eligibility criteria (e.g., CO level) upon arrival. Assessment of self-reported affective and smoking related variables will be conducted via self-report at various times throughout the session (see the orange stars on **Figure 3**).

Participants will be attached to physiological recording equipment throughout the session, including blood pressure volume, ECG, and respiration. When they smoke (in a ventilated smoking room), smoking topographical indices will be recorded using the handheld *Clinical Research Support System* (CReSS micro; described in **C.7**).

Training Conditions: Eligible participants will then be **randomized** to either the PTBT or Control (Sham Training) and informed that the training will be used in V2. **Block randomization** will be used with biological sex (female vs. male) as a blocking variable, as sex is a known factors that influences puff topography and reinforcement.^{36,58,59} Both trainings will be time-matched.

PTBT: PTBT is designed to decrease puff topography influences on smoking reward informed by heart rate variability biofeedback paradigms. Participants will be taught how to puff in a way that may feel different from their usual puffing behavior. Participants will be hooked up to a respiratory band, electrocardiogram (ECG) electrodes, and a blood volume sensor finger cuff (pulse plethysmograph) while seated in a ventilated smoking room. Following a 5-min adaptation period, they will be introduced to a breathing pacer (EZ-Air Plus; Biofeedback Foundation of Europe), which is integrated with the *Thought Technology* biofeedback interface (**Figure 4**), and taught how to use the pacer to guide the pace of their inhalation and exhalation. Participants will be taught to breathe steadily as a white ball (pacer) proceeds up the incline, and exhale as they follow the ball on the decline. They will first practice breathing normally with the pacer to ensure they understand the procedures. Then, participants will smoke following the pacer while using the CReSS micro device for a 5-min phase. To address reinforcement immediacy and intensity, the pacer will be set to a 2 sec inhalation matched with a 2 sec exhalation, for a 4 sec cycle, such that *puffing* maps onto a respiration pace of 15 breathes/min. **This pace should minimize CVC (Figure 2, right).** To address reinforcement reliability, the inter-puff-interval will vary between 4 secs and 30 secs as the experimenter will instruct the participant when to puff. In an adjacent room, the experimenter will be able to monitor real-time displays of physiological data and observe the session via video

Figure 4. Example of Biofeedback Display during PTBT

conferencing system and provide additional training instructions, as needed. Participants will then complete a 5-min rest period.

Control: In the control condition, i.e. sham training, participants will be hooked up to the same physiological monitoring equipment and complete the same 5-min adaptation period. They will then be instructed to smoking with the CreSS device while focusing their attention during a 5-min vanilla task.⁶⁶ The task involves attending to a computer screen and counting the number of times a designated color rectangle occupies the screen. Different colored rectangles are presented one at a time, for 500ms every 10 sec, for a total of 5-min. The full color spectrum is reflected and participants are told to make their best guess about color match. Participants are asked at the end to report the number of times the designated color was observed and are not given any feedback or incentive for correct color counts. No instructions will be provided about puffing behavior. Participants will then complete a 5-min rest period.

Stress-Precipitated Smoking Visit (V2). Participants will return to the laboratory on the following day, at the same time, and be provided the same pre-visit instructions. Participants will be hooked up with physiological monitoring assessment while seated in the smoking lab. Next, a new consent will be presented, introducing them to the Trier Social Stress Test (TSST), which has been used in our prior studies (R03DA041556; F31DA043934). The TSST is a well-validated laboratory paradigm that reliably induces psychological and physiological stress,⁶⁷⁻⁶⁹ including smoking craving.^{70,71} While presenting the consent form, the experimenter will explain that they will have to prepare for and deliver a speech about why they are the best candidate for a job of their choosing. To maximize anticipatory stress, participants will be introduced to a male and female confederate who will presumably observe and evaluate the speech.⁷² After a 2-min preparation period, they will be shown a video example of a speech where a participant receives negative/neutral feedback from confederates, which serves to provide participants with additional information regarding the stressful nature of the task. In our studies, this preparation/anticipatory period produces medium-large increases in negative affect in smokers (Cohen's $d = 0.60-1.30$). After the preparation period, participants are told that the confederates need additional time to trouble-shoot the camera system, and as a result they will be able to smoke before delivering the speech. Participants will be instructed that they will practice the training they learned (PTBT or Control) while they smoke, and will complete the same 5-min adaptation period pre-smoking and 5-min rest period post-smoking. The stress-precipitated smoking trial will be followed by the post-smoking assessments. Participants will then be unhooked from the physiological monitoring equipment and informed that they do not actually have to give the speech. The research staff will proceed to notify participants that they have completed the study visit. Research staff will thank participants for all of their time and effort, provide them with their respective compensation, and encourage them to contact the study staff via email or phone (contact information listed on the participant's previously provided consent form) should they have any additional questions or concerns regarding their participation.

B. Data Points

Group differences will be examined between biofeedback puffing vs. shame in response to V2 stress-precipitated smoking through measures of: (1) puff topography indices (puff volume, duration, IPI), (2) self-report assessments and (3) physiological indices of emotional distress (cardiac vagal control).

C. Study Duration

This study comprises one remote session of up to two hours, and two in-person visits over the course of two days, with a duration of up to 2 hours for V1 and V2 respectively.

D. Endpoints

The endpoint of the study is post-V2, once participants have completed the experimental design of the second visit (assuming eligibility through V1).

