1.5 Sample Size Justification

The effects of PTBT on the outcomes of interest are unclear given that there are no prior data. However, our studies of differences in puff topography in the context of acute stress vs. control produce medium-sized effects ($ds=0.46-0.54$).³⁶ Thus, we believe a medium size effect is clinically meaningful, and therefore, the sample size was calculated to detect a medium effect size difference across training groups. **Mean Difference.** For linear regression models, a sample size of 58 is sufficient to detect a medium effect size ($f^2=.143$ [R^2 change/1-cumulative R^2] = .143) with 80% power and alpha of 0.05 via multiple regression analyses with up to 10% variance explained by the main predictor (training group) and up to 5 other covariates (e.g., sex, number of cigarettes per day, depressive/anxiety symptom severity, corresponding baseline values, and CO boost) accounting for up to additional 20% of the anticipated variance. Without any covariates in the model, a sample size of 73 is needed to detect a medium effect size ($f^2=.11$) across training groups (explaining 10% variance). **Mediation (Aim 3).** Statistical power for a mediation analysis with a single mediator was estimated using Monte Carlo power analysis for indirect effects.⁸⁶ The inclusion of mediation analyses led us to increase our sample size to $n=80$, which is sufficient for detection of indirect effects with a proportion-mediated effect size of 50%⁸⁷ (correlations between predictor, mediators, and outcome, $r=.40-.43$) with 80% power and alpha of 0.05. which we deemed sufficient given the exploratory nature of these analyses. **Taken together**, to ensure analyses are adequately powered, we propose a sample of 88 (allowing for ~8-10% attrition) with a final intended sample of 80 completers (40 per condition).

[figure not shown]

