connected to a pressure transducer, which converts pressure into a digital signal that is sampled at 1,000Hz. Puff indices will be averaged and examined at puff-to-puff level. To index changes in **CVC** as a function of condition, continuous ECG and respiration data will be sampled at 1,000Hz, and differences in RSA from the 5-min adaptation period (V1) to the 5-min peri-smoking period (V2) will be derived and scored using cardiopro in accord with established guidelines.⁷³ **Smoking reinforcement** will be assessed with: **(a)** the *Short-Cigarette Purchase Task* (S-CPT),⁷⁴ a hypothetical purchase task designed for repeated assessment of cigarette (wanting), modified to purchasing of the “last cigarette smoked” to index intensity (*consumption when free*), O_{max} (*maximum expenditure on cigarettes*), and breakpoint (*point at which consumption is zero*) and **(b)** the *Modified Cigarette Evaluation Questionnaire* (mCEQ),⁷⁵ which assesses how respondents feel about the “last cigarette smoked” with subscales that tap liking (*cigarette satisfaction*), wanting (*craving reduction*), and learning (*psychological reward*).

▪ **Subject Identifiers:**

Data will be de-identified with an arbitrary ID number. Subject identifiers of name, email address, address, and phone number will be stored under lock and key and in password-protected electronic databases, separate from all data.

B. Secondary Data Collection

Additional measures administered and administration time points are included below in **Table 1**. Please refer to **Figure 3** for where these time points fall in the visit procedures. Full measures are attached for review.

Measure	Screening	Baseline (remote session)	0	Adaptation	1 1a, and 1b	Smoking	2	Rest
Phone Screen.	X							
Depression, Anxiety, and Stress Scales, 21 Item Version (DASS-21).		X						
The Mini International Neuropsychiatric Interview 7.0.0 (MINI) sections C, I, J, and K.		X						
Demographic information.		X						
Smoking History Questionnaire.		X						
Medical History Form.		X						
McCarthur Ladder for Subjective Social Status.		X						
Economic Strain Questionnaire.		X						
Fagerstrom Test for Cigarette Dependence.		X						

Mood and Anxiety Symptoms Questionnaire.		X					
Multidimensional Experiential Avoidance Questionnaire.		X					
Anxiety Sensitivity Index.		X					
Distress Tolerance Scale.		X					
Distress Intolerance Index.		X					
Brief WISDM.		X					
Positive And Negative Affect Schedules (PANAS).		X					

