Test of Aim 2: The effects of PTBT vs. Control on acute smoking reinforcement (i.e., cigarette purchase task [S-CPT], cigarette satisfaction/reward [mCEQ]) following stress-precipitated smoking will be estimated using separate linear regression models with group predicting each outcome. Planned covariates include the baseline value of the outcome when relevant (S-CPT), biological sex, number of cigarettes per day, and DASS-21, and the models will be tested with and without covariates. Effect size (d) will also be calculated.

Test of Aim 3 (Exploratory Analyses): Differences in CVC (via RSA) between training groups during the stress-precipitated smoking trial will be tested using linear regression models, controlling for baseline levels. Training group will be used to predicting CVC (outcome). Covariates will be identical to those in prior analyses, and will be tested with and without covariates, and effect size (d) will be calculated.

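### As written, the RSA baseline for Aim 3 is recorded after randomization, so randomization does not guarantee that it is unaffected by allocation

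*Combined protocol and SAP*

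**What the plan says.** Section 1.3 A describes V1 in this sequence: a final eligibility check on arrival, then randomization blocked by sex "to either the PTBT or Control (Sham Training) and informed that the training will be used in V2", then the procedures of each condition. The adaptation period appears inside those condition descriptions. For PTBT: "Following a 5-min adaptation period, they will be introduced to a breathing pacer". For Control, participants are connected to the same equipment and "complete the same 5-min adaptation period" before the colour-counting task. Section 1.6 A repeats the order.

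Section 1.9 A (Study Instruments) defines the CVC measure as "differences in RSA from the 5-min adaptation period (V1) to the 5-min peri-smoking period (V2" visits. Section 6.1 states that Aim 3 group differences in RSA "will be tested using linear regression models, controlling for baseline levels". It labels Aim 3 exploratory and does not say which recording supplies the baseline. V2 has its own 5-minute adaptation period before smoking.

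**The concern.** A baseline covariate is safe to adjust for because it is fixed before allocation, so the arms can differ on it only by chance. In the written order the Aim 3 baseline lacks that protection. RSA follows breathing, as section 1.4 explains, and breathing is what PTBT sets out to pace. If knowing the allocation altered how participants breathed at rest, or how staff handled them, the two baselines could differ systematically. The analysis would then remove part or all of that difference from the V2 contrast and report the result as a training effect.

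The sign matters too. Aim 3 predicts a greater fall in CVC under PTBT. A raised PTBT baseline would favour that hypothesis, and a lowered one would mask a true effect. Nothing in the plan requires this exposure, because the adaptation period is the same in both arms.

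**Working it through.** **The plan's own figures.** Section 1.5 sizes the regressions "with 80% power and alpha of 0.05 via multiple regression analyses", "with up to 10% variance explained by the main predictor (training group") and covariates "accounting for up to additional 20% of the anticipated variance".

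- With covariates: f² = 0.10/0.70 = 0.143. A noncentral F test of one predictor among six gives N = 58 (power 0.806), as stated.
- Without covariates: f² = 0.10/0.90 = 0.111 gives N = 73 (power 0.802), as stated.
- Attrition: 80/(1 − 0.09) = 87.9, so 88, as stated.

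These reproduce. They do not bear on the order of steps, and the fix changes none of them.

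**The order, step by step.** (1) Eligibility check. (2) Randomization, with notice that the training will be used in V2. (3) Adaptation recording, described under the assigned condition. (4) Pacer or colour-counting task. Section 1.9 A makes step 3 the baseline, and step 3 follows step 2.

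**Bias if the baseline shifts.** Let δ be the shift in PTBT minus Control baseline RSA caused by allocation, in SD units. Let ρ be the within-arm slope of V2 RSA on baseline, which equals the correlation when the SDs are equal. Assume the shift touches the baseline only, and the true training effect is zero.

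- Adjusted contrast = (difference in V2 means) − ρ × (difference in baseline means). Its expectation is 0 − ρδ = −ρδ.
- Change score = (difference in V2 means) − (difference in baseline means). Its expectation is −δ.
- A V2 comparison with no baseline term does not carry this bias.

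With 40 per arm, the standard error of the adjusted contrast is √[(1 − ρ²) × 2/40]. This is √(0.75 × 0.05) = 0.194 at ρ = 0.5 and √(0.51 × 0.05) = 0.160 at ρ = 0.7. The documents give neither ρ nor δ, so the rows below are assumptions. Type I error is two-sided at nominal 5%, by normal approximation.

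| ρ | δ (SD) | Size of bias, ρδ (SD) | Bias / SE | Type I error |
|---|---|---|---|---|
| any | 0 | 0 | 0 | 5.0% |
| 0.5 | 0.1 | 0.05 | 0.26 | 5.8% |
| 0.5 | 0.2 | 0.10 | 0.52 | 8.1% |
| 0.7 | 0.1 | 0.07 | 0.44 | 7.2% |
| 0.7 | 0.2 | 0.14 | 0.88 | 14.2% |

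**Simulation check** (4,000 replicates, 40 per arm). At ρ = 0.5 and δ = 0.2, the adjusted bias was −0.101, type I error 7.7%, and the change-score bias −0.200. At ρ = 0.5 and δ = 0, the bias was 0.001 and type I error 5.2%. The formulas hold.

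**After the fix.** If the recording precedes allocation, δ from allocation is zero by design, whatever ρ is.

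**The case against.** The strongest reply is that nothing has happened to participants by the time of the adaptation recording. Sensors and adaptation are the same in both arms, and the pacer and the colour task come afterwards. That stands. It confines any shift to expectation or staff behaviour, leaves its sign unknown, and makes a value near zero quite plausible.

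A reader might infer that participants already know they will be taught to puff differently. The documents do not support this. They say only that participants are told the training will be used in V2, and are silent on whether the arm or its content is disclosed before adaptation. Equally, the sections available describe no concealment or staff blinding that would rule out an influence at that point.

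The order is also less certain than the prose suggests. Section 1.3 A says recording equipment is worn throughout the session before it mentions randomization. It refers to Figure 3 for the sequence, and that figure was not available to this review. Table 1 has an adaptation column but does not place randomization. The order should therefore be confirmed as part of the fix.

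A reader might add that unusable ECG or respiration signals would be found only after randomization, causing avoidable loss. The documents give no rate for this, and section 1.5 already allows about 8–10% attrition. Screening on signal quality could also exclude people who can contribute to Aims 1 and 2, whose outcomes do not use RSA. That argument is not relied on here.

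**Conclusion.** The point holds in a limited form. In the written order the Aim 3 baseline follows randomization, so the design does not guarantee that it is free of an allocation effect. The documents do not show that any such effect exists, and it would be wrong to say the Aim 3 contrast is biased.

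On the assumed ranges (shift 0.1–0.2 SD, slope 0.5–0.7), the bias in the adjusted contrast would be 0.05–0.14 SD and type I error about 6–14%. A change score would be off by the full 0.1–0.2 SD. With no shift, the bias is zero.

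Severity is low to moderate, since only an exploratory aim is affected. The change is still worth making because it costs almost nothing and replaces an assumption with a guarantee. Separately, section 6.1 needs to name its baseline in any case, because both visits include an adaptation period.

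**What to change.** 1. In sections 1.3 A and 1.6 A, state that sensors are attached and the 5-minute V1 adaptation period is recorded before the sex-blocked allocation is opened or disclosed to the participant or to the staff running the session. Align the text with Figure 3. If the figure already shows this order, only the prose needs correcting.
2. Do not make signal quality a condition of randomization, so that participants with poor ECG or respiration data remain available for Aims 1 and 2.
3. In section 6.1, name the pre-randomization V1 adaptation RSA as the Aim 3 baseline, and say whether it enters as a covariate or through a change score.

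Cost: two V1 steps change places and about one sentence is added to 6.1. The documents describe nothing that requires allocation to come first. There is no additional visit or measurement, and the figures of 58, 73, 80 and 88 all stand.
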